8.6.2. Clinical Laboratory Parameters

All clinical laboratory parameters and their changes from baseline will be listed; any value outside the clinical reference range will be flagged, and whether the out of range value was deemed clinically significant or not clinically significant will be indicated.

Summary tables by treatment and timepoint will be provided for clinical chemistry, hematology, and coagulation parameters, and their changes from baseline, as applicable.

Values recorded as $\langle x, \leq x, \rangle x$, or $\geq x$ will be displayed in the listings as recorded. For the derivation of listing flags, all calculations, $\langle x \rangle x$ and $\leq x \rangle x$ values will be set to x.

8.6.3. Vital Signs Parameters

All vital signs parameters and their changes from baseline will be listed, as applicable; any value outside the clinical reference range will be flagged, and whether the out of range value was deemed clinically significant or not clinically significant will be indicated.

Summary tables by treatment and timepoint will be provided for all vital signs parameters and their changes from baseline, as applicable.

8.6.4. 12-lead Electrocardiogram Parameters

All 12-lead ECG parameters and their changes from baseline will be listed; any value outside the clinical reference range will be flagged, and whether the out of range value was deemed clinically significant or not clinically significant will be indicated.

Summary tables by treatment and timepoint will be provided for all 12-lead ECG parameters, along with their changes from baseline.

QT interval corrected for heart rate using Fridericia's formula (QTcF) values that are > 450 msec and increase from baseline > 30 msec will be flagged in the data listing.

8.6.5. Other Assessments

Medical history, physical examination and digoxin concentrations will be listed. Any physical examination abnormalities reported and abnormal digoxin concentrations will also be flagged as clinically significant or not clinically significant as indicated.

All other safety and tolerability assessments not detailed in the above sections will be listed only.

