2.2.2. Secondary Endpoints

Safety and tolerability will be assessed by monitoring AEs, performing physical examinations and clinical laboratory evaluations, measuring vital signs, recording 12-lead ECGs, and safety monitoring of serum digoxin levels.

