8.4. Safety Analysis

All safety assessments, including AEs, SAEs, vital sign measurements, clinical laboratory results, safety monitoring of serum digoxin levels, physical examination results, concomitant medications, and 12-lead ECGs, will be tabulated and summarized where possible, using descriptive methodology by treatment, as needed, by timepoint. Unless otherwise specified, baseline value is defined as the last non-missing measurement before administration of study drug on Day 1. No formal statistical analyses are planned for the safety data. All safety data will be listed by subject.

Concomitant medications will be coded using the World Health Organization (WHO) Drug Dictionary (WHO Drug Global B3, September 2019). Adverse events will be coded using Medical Dictionary for Regulatory Activities (MedDRA) Version 22.1 (or higher). The incidence of AEs will be presented by severity and by relationship to study drug as determined by the Investigator or designee (Appendix 1 for AE reporting). All TEAEs will be summarized by system organ class and preferred term.

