Appendix 2: Clinical Laboratory Evaluations

| Clinical Chemistry Panel (Fasted): | Hematology Panel: | Other Tests: | | | | |
|---|--|---|--|--|--|--|
| Alanine aminotransferase (ALT) Albumin Alkaline phosphatase (ALP) Amylase Aspartate aminotransferase (AST) Bilirubin (direct and total) Blood urea nitrogen Calcium Chloride Cholesterol Creatine kinase Creatinine Glucose Iron Lipase Magnesium Phosphorus Potassium Sodium Total protein Triglycerides Uric acid | Hematocrit Hemoglobin Mean corpuscular hemoglobin Mean corpuscular hemoglobin concentration Mean corpuscular volume Platelet count Red blood cell (RBC) count RBC distribution width White blood cell (WBC) count WBC differential (percent and absolute): Basophils Eosinophils Lymphocytes Monocytes Neutrophils | Hemoglobin A1c (HbA1c) ^b Thyroid-stimulating hormone (TSH) ^b Estimated glomerular filtration rate ^{a,d} SARS-CoV-2 (COVID-19) test Safety digoxin levels (serum) Coagulation Parameters: Partial thromboplastin time Prothrombin time International normalized ratio Serology ^b : Hepatitis B surface antigen (HBsAg) Hepatitis B virus (HBV) immunoglobulin M (IgM) core antibody Hepatitis C virus (HCV) antibody Human immunodeficiency virus (HIV) antibody | | | | |
| | Urinalysis: Bilirubin | For Female Subjects Only: Pregnancy test (qualitative serum or qualitative urine, quantitative serum human chorionic gonadotropin tests may be used | | | | |
| Urine Drug Screen ^a : Including but not limited to the following: Alcohol (ethanol) ^e Amphetamines Barbiturates Benzodiazepines Cannabinoids Cocaine (metabolite) Methadone Opiates Phencyclidine Cotinine | Color and appearance Glucose Ketones Leukocyte esterase Nitrite Occult blood pH and specific gravity Protein Urobilinogen Microscopic examination including bacteria, casts, crystals, epithelial cells, RBCs, and WBCs (if protein, leukocyte esterase, nitrite, or occult blood is positive) | for confirmation as needed and post-menopausal subjects may be eligible for participation if the results of the qualitative serum pregnancy or qualitative urine pregnancy test are positive but the quantitative serum human chorionic gonadotropin results are within the laboratory's reference ranges for post-menopausal women) ^c Follicle-stimulating hormone (post-menopausal female subjects only) ^b | | | | |

- a. Performed at Screening and Check-in (Day -1) only.
- b. Performed at Screening only.

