1. INTRODUCTION

This SAP has been developed after review of the clinical study protocol (Final Version 1.0 dated 12 February 2021) and electronic case report form (eCRF).

This SAP describes the planned analysis of the pharmacokinetic (PK), safety, and tolerability data from this study. A detailed description of the planned TFLs to be presented in the clinical study report (CSR) is provided in the accompanying TFL shells document.

In general, the analyses are based on information from the protocol, unless they have been modified by agreement with Loxo Oncology, Inc. A limited amount of information about this study (eg, objectives, study design) is given to help the reader's interpretation.

This SAP must be finalized prior to the lock of the clinical database. Additionally, the SAP and TFL shells should be finalized prior to any programming activities commencing.

This SAP supersedes any statistical considerations identified in the protocol; where considerations are substantially different, they will be so identified. If additional analyses are required to supplement the planned analyses described in this SAP, they may be performed and will be identified accordingly in the CSR. Any substantial deviations from this SAP will be agreed with Loxo Oncology, Inc. and identified in the CSR.

This SAP is written with consideration of the recommendations outlined in the International Conference on Harmonisation (ICH) E3 guideline *Structure and Content of Clinical Study Reports*, ICH E8 guideline *General Considerations for Clinical Trials*, ICH E9 guideline *Statistical Principles for Clinical Trials*. ^{1,2,3}

The document history is presented in Appendix 1.

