3.2. Secondary Endpoints

Safety and tolerability will be assessed by monitoring adverse events (AEs), performing physical examinations and clinical laboratory evaluations, measuring vital signs, recording 12-lead electrocardiograms (ECGs), and safety monitoring of serum digoxin levels.

[figure not shown]

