10. SIGNIFICANT CHANGES FROM THE PROTOCOL-SPECIFIED ANALYSES

The primary endpoint "area under the concentration-time curve from hour 0 to 24 hours (AUC0-24)" has been removed as this is a repeat of the following primary endpoint "area under the concentration-time curve over a dosing interval (AUC_{tau})" since for this study tau is equal to 24 hours.

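### Does it matter that the SAP lists serum digoxin safety levels when the protocol speaks of summarising them?

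*SAP*

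**What the plan says.** Both documents place serum digoxin monitoring under the secondary endpoints, as one of several means of assessing safety and tolerability. Protocol Section 2.2.2 ends its list with "recording 12-lead ECGs, and safety monitoring of serum digoxin levels", and SAP Section 3.2 with "recording 12-lead electrocardiograms (ECGs), and safety monitoring of serum digoxin levels".

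Protocol Section 8.4 says that the safety assessments, including "clinical laboratory results, safety monitoring of serum digoxin levels, physical examination results, concomitant medications, and 12-lead ECGs, will be tabulated and summarized where possible", are to be handled descriptively by treatment and, if needed, by timepoint. It says separately that all safety data will be listed by subject. The protocol synopsis repeats this and leaves the specific procedures to the SAP.

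SAP Section 8.6.5 states: "Medical history, physical examination and digoxin concentrations will be listed". Its next sentence adds that abnormal digoxin concentrations will be flagged as clinically significant or not. The laboratory tables in SAP Section 8.6.2 do not cover digoxin: "Summary tables by treatment and timepoint will be provided for clinical chemistry, hematology, and coagulation parameters".

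On departures from the protocol, SAP Section 1 says that "where considerations are substantially different, they will be so identified". SAP Section 10 records one change, the AUC0-24 endpoint, which "has been removed as this is a repeat of the following primary endpoint".

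**The concern.** Protocol Section 1.6 says that digoxin has a narrow therapeutic window and presents daily serum levels as a safety measure. Protocol Section 7.2.6 sets a trough of 2.0 ng/mL above which a subject may be discontinued. One would expect a table of troughs before and after LOXO-305 starts, with a count above 2.0 ng/mL. The protocol appears to promise the table, the SAP does not plan it, and the section of the SAP meant for such changes is silent.

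There is also a possible link to the primary analysis. A subject discontinued for a high trough between Days 9 and 15 can contribute to the Day 8 single-dose comparison but has no Day 16 profile. If LOXO-305 raises digoxin exposure and the strongest responders leave, the Day 16 ratio would be pulled toward no effect. A reader might want a table that shows whether this happened.

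**Working it through.** The plan states no figure to reproduce. The check has two parts: whether a summary is feasible, and what would be lost without one.

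**Feasibility.**

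- Scheduled samples per subject: predose on Days 7 to 15 (Protocol Appendix 4, note q), so 15 − 7 + 1 = 9. This agrees with the 9 digoxin safety samples in Protocol Appendix 3.
- Subjects: up to 16 (Protocol Section 8.1), so at most 9 × 16 = 144 values.
- LOXO-305 starts on Day 8, after that day's predose sample. Days 7 and 8 are therefore digoxin alone, 2 × 16 = 32 values. Days 9 to 15 are on the combination, 7 × 16 = 112 values.
- Each day has up to 16 values. SAP Section 8.1.2 requires at least 3 for full summary statistics.

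A summary by day and by both safety treatment labels in SAP Table 1 is thus possible, and the protocol's qualifier about feasibility does not account for its absence.

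**What a reader has if the SAP is followed exactly.**

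| Question | Where the plan answers it |
|---|---|
| What were the individual troughs? | Listing of digoxin concentrations (SAP 8.6.5) |
| Which abnormal values mattered clinically? | Clinical-significance flag (SAP 8.6.5) |
| Are early leavers included? | Yes; listings run to completion or discontinuation (SAP 8.1) |
| How many subjects left the study? | Disposition summary table (SAP 8.2); the reason is recorded on the eCRF (Protocol 4.6) |
| How many left because of an adverse event? | Treatment-emergent events leading to discontinuation, by treatment (SAP 8.6.1) |
| How many subjects lack a Day 16 profile? | n by treatment in the PK parameter tables (SAP 8.5.2), where single-dose and multiple-dose LOXO-305 have separate labels (SAP Table 2) |
| How far does LOXO-305 change digoxin exposure? | Mixed-model ratios for AUC and Cmax (SAP 8.5.3) |

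Two items have no table of their own: the number of subjects above 2.0 ng/mL, and the number without a Day 16 profile for that reason. The first can be counted from a listing of at most 16 subjects with 9 scheduled values each. The second follows by setting that listing beside the disposition data.

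**Effect on the Day 16 ratio.** Protocol Section 7.2.6 excludes the safety samples from the PK evaluation, so the model in SAP Section 8.5.3 is the same with or without a table. Any selection from discontinuation would also be the same. Its size cannot be worked out from the documents, which give no trough distribution, no variability and no likelihood of discontinuation. I attach no figure to it.

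**The case for a change.** The strongest argument for a change is that a commitment was dropped without being declared. The protocol names this assessment expressly and promises a listing as a separate matter, so a listing alone does not meet it. Vital signs and ECGs, named in the same protocol sentence, do receive tables by treatment and timepoint in the SAP. Among the items left as listings, serum digoxin is the one that is numeric, repeatedly scheduled and tied to a protocol threshold.

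As a reading of the texts this stands. A line in SAP Section 10 would have been tidier.

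It carries less weight as a reason to amend. The protocol sentence is a blanket statement with qualifiers, and it also covers physical examination and concomitant medications, which the SAP likewise only lists (Sections 8.6.5 and 8.4). The SAP promises to identify differences that are substantial, and the form in which up to 16 subjects' monitoring values are displayed can fairly be judged not to be. Protocol Appendix 2 groups serum digoxin with tests such as HbA1c and TSH, for which the SAP plans no summary either. A count above 2.0 ng/mL and a footnote to the ratio table would go beyond anything Protocol Section 8.4 promises. The table, figure and listing shells are a separate document that I have not seen; they may settle the presentation.

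**Conclusion.** The protocol and SAP differ on how serum digoxin levels are presented, and the difference is undeclared. It is a minor documentation mismatch. At most 144 values appear in a flagged listing with no accompanying summary table. No estimate, confidence interval or safety conclusion becomes wrong, and the daily review that protects subjects does not depend on any end-of-study table. Possible loss of high responders before Day 16 is a fair point to keep in mind when reading the multiple-dose ratio, but a descriptive table would not reduce it, and the planned outputs already reveal missing Day 16 subjects.

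This rests on two assumptions: the listing contains every scheduled value, as SAP Section 8.1 provides, and the disposition data carry the withdrawal reason recorded on the eCRF. An analyst who wishes to add a table by day when writing the report can do so from data already collected, since SAP Section 1 allows supplementary analyses identified as such. The plan can stand as written.

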8.6.6. Safety and Tolerability Statistical Methodology

No inferential statistical analyses are planned.

9. INTERIM ANALYSES

No interim analyses are planned.

10. SIGNIFICANT CHANGES FROM THE PROTOCOL-SPECIFIED ANALYSES

The primary endpoint "area under the concentration-time curve from hour 0 to 24 hours (AUC0-24)" has been removed as this is a repeat of the following primary endpoint "area under the concentration-time curve over a dosing interval (AUC_{tau})" since for this study tau is equal to 24 hours.

